7.9.6 ECG Parameters

For each ECG parameter, descriptive statistics of the observed values as well as change from study baseline will be presented overall for each assessment timepoint for the safety population. Shift tables from study baseline to the discharge visit (Day 15) for the overall ECG interpretation (normal, abnormal not clinically significant, or abnormal clinically significant) will be summarized for all subjects in the Safety population.

ECG parameters will also be presented in a data listing.

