3. Patient has evidence of severe or active end-organ damage attributable to diabetes (eg, active diabetic nephropathy, retinopathy, or neuropathy) at the Screening Visit or Check-in.
4. Patient has evidence of active end-organ morbidity associated with uncontrolled hypertension (eg, progressive kidney insufficiency, myocardial infarction, or stroke) at the Screening Visit or Check-in. Patient has had an in-patient hospitalization for a cardiovascular, renal, or metabolic cause in the 6 months before the Screening Visit.
5. Patient has orthostatic decrease in systolic BP of > 20 mm Hg or orthostatic decrease in diastolic BP of > 15 mm Hg.
6. Patient has severe renal insufficiency (eg, current or past need for dialysis) has undergone renal transplantation, or has planned renal transplantation.
7. Patient has a history of malignancy, diagnosed or known to be active or actively treated within the past 5 years, other than resected lesions of low malignant potential, such as basal cell skin cancers.
8. Patient has bleeding diathesis or history of clinically significant bleeding episodes (eg, gastrointestinal bleed) in the 12 months before the Screening Visit.
9. Patient has a 12-lead ECG demonstrating severe bradycardia (heart rate < 40 beats per minute) or QTcF is \geq 450 msec for male patients or is \geq 470 msec for female patients at the Screening Visit. (**Note:** If on initial ECG, QTcF exceeds the limit, the ECG will be repeated 2 more times, and the average of the 3 QTcF values will be used to determine the patient's eligibility).
10. Patient has alanine aminotransferase (ALT) or aspartate aminotransferase (AST) level > 2 times the upper limit of normal as defined by the laboratory or creatinine level > 1.5 times the normal as defined by the laboratory at the Screening Visit.

11. Patient has a history of clinically significant hypersensitivity or allergies to any of the inactive ingredients contained in the active or placebo drug products.
12. Patient has a history of active alcoholism or drug addiction during the year before the Screening Visit, or has a positive drug screen at the Screening Visit or at Check-in.
13. Patient has previously received IW-1973 in a study or has received an investigational drug during the 30 days or 5 half-lives of that investigational drug (whichever is longer) before the Screening Visit or is planning to receive another investigational drug at any time during the study.

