3.5.4 Selection and Timing of Dose for Each Patient

All patients will receive 2 orally administered doses per day: an AM dose and a PM dose. Except for Day 13, patients will receive the AM dose at approximately the same time (\pm 15 minutes) every day in the morning (8 to 10AM) following an overnight fast of \geq 8 hours. (Note: For each patient, the first dose on Day 1 may be administered between 8 and 10AM; thereafter, AM doses on Days 2 to 12 and on Day 14 must be administered within 15 minutes of the time of dosing on Day 1.) On Day 13, first dose should be administered in the morning between 7 and 10:30AM,

after the EndoPAT assessment (when applicable). Breakfast should begin within 30 minutes after dosing. Each patient will receive their PM dose 12 hours (\pm 30 minutes) after their AM dose and at least 30 minutes after completing a normal dinner.

Patients may take multiple tablets together. Permitted concomitant may be taken at the same time as study drug.

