AM = morning; BP = blood pressure; h = hour; H = height; HBsAg = hepatitis B surface antigen; HCV = hepatitis C virus; HIV = human immunodeficiency virus; ICF = informed consent form; m = minute; msec = millisecond; pd = postdose; pdD1 = corresponding to postdose Day 1; PM = evening; pre = predose; preD1 = corresponding to predose Day 1; R = respiratory rate; T = oral temperature; W = weight

- Urine drug screen for selected drugs of abuse and alcohol breathalyzer screen
- For female patients, a negative serum pregnancy test must be documented at the Screening Visit, at Check-in with results available before randomization, and at the Follow-up Visit. A urine pregnancy test must be documented at the End of Trial Visit.
- On in-clinic days, in the morning after voiding, before any water or food intake
- Patients must be supine for ≥ 5 minutes before the ECG recording (Note: If on initial ECG, QTcF is ≥ 450 msec for male patients or is ≥ 470 msec for female patients, the ECG will be repeated 2 more times, and the average of the 3 QTcF values will be used to determine the patient's eligibility).

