7.9.5 Additional Vital Signs Parameters

Vital signs evaluations at each assessment timepoint not included in the PD analyses (ex. standing blood pressure and pulse assessments) and the corresponding change from study baseline will be summarized for each treatment group and presented in a data listing.

The number and percentage of patients who had a notable change from baseline in BP and pulse (based on the criteria in [Table 4](#)), will be presented by treatment group.

Table 4. Criteria for Notable Changes in Post-Baseline Vital Signs

Vital Sign Parameter	Flag	Criteria*	
		Observed Value	Change from Study Baseline
Supine/Standing Systolic Blood Pressure (mmHg)	High	≥ 180	Increase of ≥ 30
	Low	≤ 90	Decrease of ≥ 30
Supine/Standing Diastolic Blood Pressure (mmHg)	High	≥ 105	Increase of ≥ 20
	Low	≤ 50	Decrease of ≥ 20
Supine Pulse Rate (bpm)	High	≥ 110	Increase of ≥ 20
	Low	≤ 50	Decrease of ≥ 20
Standing Pulse Rate (bpm)	High	≥ 120	Increase of ≥ 25
	Low	≤ 50	Decrease of ≥ 20

*A postbaseline value is considered as a notable value if it meets both criteria for observed value and change from baseline.

Orthostatic BP Measurements

Orthostatic changes in systolic BP, diastolic BP, and pulse will be summarized for each treatment group. An orthostatic measurement is obtained by subtracting the supine measurement from the standing measurement.

The number and percentage of patients who meet the following criteria at any postdose timepoint will also be summarized by treatment group:

- Orthostatic decrease in systolic BP of > 20 mmHg from supine to standing
- Orthostatic decrease in diastolic BP of > 15 mmHg from supine to standing
- Orthostatic increase in pulse of > 30 beats per minute from supine to standing

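### SAP 7.9.6 words ECG results as overall although the protocol asks for them by treatment group, and plans no QTcF patient counts or baseline-adjusted placebo difference: a cheap improvement, not a missed safety rule

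*SAP*

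**What the plan says.** SAP 7.9.6 plans three ECG outputs:

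- For each parameter, "descriptive statistics of the observed values as well as change from study baseline will be presented overall for each assessment timepoint", in the Safety Population.
- "Shift tables from study baseline to the discharge visit (Day 15) for the overall ECG interpretation", a three-level rating, summarised for everyone in the Safety Population.
- A listing: "ECG parameters will also be presented in a data listing".

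Protocol 3.9.3.4.2 has ECG values and changes from study baseline summarised by treatment group. SAP 6.1 makes by-arm plus pooled IW-1973 the default for safety summaries, unless a section indicates otherwise. It also includes quartiles, minimum and maximum among the descriptive statistics, and defines study baseline as the last value before the first dose.

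The Schedule of Events has two post-dose ECGs: 4 hours after the Day 1 AM dose, and Day 15.

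Other safety measures get patient counts. Under SAP 7.9.5, "The number and percentage of patients who had a notable change from baseline in BP and pulse" is tabulated by treatment group, as are patients passing orthostatic limits. ANCOVA with a placebo difference is confined to PD endpoints (SAP 6.2 and 7.7.2).

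The QTcF limits appear in Protocol Exclusion 9 and in the schedule's ECG footnote: "QTcF is ≥ 450 msec for male patients or is ≥ 470 msec for female patients" triggers two repeats, and "the average of the 3 QTcF values will be used to determine the patient's eligibility".

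**The concern.** The stated objective is to compare the safety of two regimens. For ECG, three things needed for that comparison are absent or unclear.

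1. **Grouping.** Read literally, SAP 7.9.6 pools active and placebo patients, contrary to the protocol.
2. **Patient-level tabulation.** The only categorical output is a global rating, and it runs only to Day 15. The Day 14 PM dose is placebo in both active arms, so Day 15 falls about a day after the last active dose. The 4-hour Day 1 ECG is the only scheduled one within hours of an active dose, and it has no categorical summary.
3. **Placebo contrast.** No difference from placebo is planned. The Day 1 predose ECG follows an overnight fast of at least 8 hours, and "Breakfast should begin within 30 minutes after dosing", so the 4-hour ECG comes after a meal and later in the day. Change within an arm therefore combines those influences with any drug effect.

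At stake is how clearly a QTcF effect, or its absence, can be attributed to a regimen, and whether the definition of a notable QTcF value is fixed before unblinding.

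**Working it through.** **Inputs.** From the documents: 26 patients randomised 5:5:3, so 26 × 5/13 = 10, 26 × 5/13 = 10 and 26 × 3/13 = 6. The documents give no QTcF SD and no pre/post correlation (rho). I assume SD 15-20 msec and rho 0.5-0.8 as ranges.

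**1. Effect of pooling.** Let d be a mean drug shift common to both active arms, and m the average effect of meal and time of day, common to all arms.

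- Pooled mean change = (20/26)d + m = 0.77d + m. Neither d nor a difference between regimens can be recovered from it.
- By arm: active change minus placebo change = (d + m) − m = d.

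By-arm output with a placebo contrast is therefore what removes the meal effect. The baseline covariate is not needed for that.

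**2. One large individual change.** A patient with +60 msec moves the mean of 26 by 60/26 = 2.3 msec and that of a 10-patient arm by 60/10 = 6 msec. The same value would stand as the maximum, or close to it, in the planned table.

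**3. What counts can show.**

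- At a true outlier rate of 10%, the chance of at least one in a 10-patient arm is 1 − 0.9^10 = 65%. At 5% it is 40%, and at 20% it is 89%.
- With no events observed, the two-sided 95% exact upper limit is 30.8% for 0/10 and 45.9% for 0/6.
- Against 0/6 on placebo, the smallest count in one arm with Fisher p ≤ 0.05 is 6/10 (p = 0.034).

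Counts at this size describe individuals and give little between-arm inference.

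**4. What the covariate adds.**

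- SE of the baseline difference, 10 versus 6: SD × sqrt(1/10 + 1/6) = 0.516 × SD, or 7.7 msec (SD 15) to 10.3 msec (SD 20).
- A one-SE chance imbalance leaves (1 − rho) × SE in the change-score difference: 0.2 × 7.7 = 1.5 msec (SD 15, rho 0.8) to 0.5 × 10.3 = 5.2 msec (SD 20, rho 0.5).
- Relative to the SE of that difference, this is sqrt((1 − rho)/2) = 0.32 (rho 0.8) to 0.50 (rho 0.5).
- SE ratio, ANCOVA to change score: sqrt((1 + rho)/2) = 0.949 (rho 0.8) to 0.866 (rho 0.5), that is 5-13% smaller.
- 95% half-width for one active arm minus placebo at SD 15, ignoring the imbalance term. Change score: t(23 df) × SD × sqrt(2(1 − rho)) × 0.516. ANCOVA: t(22 df) × SD × sqrt(1 − rho²) × 0.516. At rho 0.7 it goes from 12.4 to 11.5 msec, and at rho 0.5 from 16.0 to 13.9 msec.

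**5. Precedent for reusing an eligibility limit.** Exclusion 5 bars orthostatic falls above 20 mm Hg systolic or 15 mm Hg diastolic. SAP 7.9.5 counts patients passing the same two figures at any post-dose timepoint, by treatment group. Exclusion 9's QTcF limits have no such counterpart in SAP 7.9.6.

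**6. Limit of an absolute count.** A man going from 385 to 445 msec (+60) is not counted at 450, while one going from 449 to 451 (+2) is. A category for increase from baseline is needed as well.

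**The case against.** The case against is substantial, and most of it stands.

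- **A reader might infer that the plan ignores its own post-dose QTcF limit.** It has none. The 450/470 msec values decide eligibility, and so does the repeat-and-average rule. Using them after dosing is a new analysis choice, though one in line with SAP 7.9.5.
- **A reader might infer that a prolongation would go unseen.** The minimum, maximum and listing would show it. Changes that the investigator judges clinically significant are reported as AEs (Protocol 3.7.3.9). What is missing is a tabulation by arm with a cut-off fixed beforehand.
- **A reader might infer that baseline is ignored.** SAP 7.9.6 already includes change from study baseline. Only covariate adjustment is absent.
- **A reader might infer that concomitant medication confounds the change.** The rule that measurements precede oral and antihypertensive medication is written for predose BP and EndoPAT (Protocol 3.5.7 and 3.7.3.2), not for ECG (3.7.3.3). The documents establish the meal, not the medication.
- **A reader might infer that the sponsor means to pool the arms.** That is not settled. SAP 7.9.2 uses the same word for laboratory values, and SAP 8 lists no change from the protocol's by-arm ECG summaries. The wording may be standing text, but it could also be read as an exception to the SAP 6.1 default.

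The SAP also calls safety analyses qualitative (6.6) and any inference descriptive (6.1). That argues for labelling the additions descriptive, not for leaving them out.

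**Conclusion.** The point holds as a low-severity improvement. The wording conflict between SAP 7.9.6 and Protocol 3.9.3.4.2 is the most consequential part, because a pooled presentation would show 0.77 of a common active-arm shift and offer no placebo contrast. Next come the missing patient-level QTcF counts, above all at 4 hours on Day 1. Covariate adjustment is a modest gain: 5-13% smaller standard error at assumed rho 0.8-0.5, with chance-imbalance carry-over of 1.5-5.2 msec at assumed SD 15-20 msec, at most half a standard error of the difference for a one-SE imbalance. These figures rest on assumed SD and rho; the 0.77 follows from the allocation, taking equal shifts in the two active arms.

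**What to change.** In SAP 7.9.6:

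1. Reconcile the wording with Protocol 3.9.3.4.2, so that ECG summaries and shift tables are by treatment group and for IW-1973 overall.
2. Add by-arm descriptive counts at Day 1 4 hours and Day 15 of patients with QTcF at or above 450 msec (men) or 470 msec (women) who were below the limit at study baseline. Add a category for increase from baseline. The documents give no cut-off for it, so the sponsor should fix one before unblinding. State which reading counts when an ECG is repeated, since SAP 9.1 uses the last measurement for summaries but all measurements for notable values.
3. Apply the SAP 7.7.2 ANCOVA to QTcF at both timepoints, giving each IW-1973 arm minus placebo with a 95% CI, labelled descriptive.

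The cost is a wording change, one small table and reuse of an existing model, with no new ECGs or readings. The downside is a few more descriptive intervals, wide at 10 versus 6.

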3.5.3 Selection of Dosage in the Study

This Phase 2a exploratory study will evaluate 40 mg IW-1973 administered daily for 2 weeks according to 2 different regimens: QD for both weeks or BID for the 1st week and QD the 2nd week. In the Phase 1b MAD study ([ICP-1973-102](#)), 40 mg IW-1973 was considered the maximum tolerated repeat dose, therefore, 40 mg was chosen for evaluation in this patient population.

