3.5.5 Dosage

On Days 1 to 14, all patients will receive 2 daily 8-tablet doses (AM and PM), 12 hours (\pm 30 minutes) apart.

Matching placebo tablets will be administered with IW-1973 Tablets when required to mask treatment assignments. [Table 3](#) outlines study drug dosage by week and time, for each regimen/treatment arm.

Table 3. Dosage by Week and Time for Each Treatment Arm

Regimen/ Treatment arm	Dose time	Dosage Days 1 to 7	Dosage Days 8 to 14
QD/QD	AM	8 x IW-1973 Tablet	8 x IW-1973 Tablet
	PM	8 x placebo tablet	8 x placebo tablet
BID/QD	AM	4 x IW-1973 Tablet 4 x placebo tablet	8 x IW-1973 Tablet
	PM	4 x IW-1973 Tablet 4 x placebo tablet	8 x placebo tablet
PBO/PBO	AM	8 x placebo tablet	8 x placebo tablet
	PM	8 x placebo tablet	8 x placebo tablet

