3.8.2.2 Day -1

- Weight
- If planned, EndoPAT assessment completed > 30 minutes before the time corresponding to AM dose on Day 13 and before all oral and any antihypertensive concomitant medications (Note: For each patient, the Day -1 and Day 13 assessments should occur at approximately the same time of day [± 15 minutes])
- Respiratory rate and oral temperature
- Collection of urine samples:
 - Urine albumin and creatinine (first void)
- Supine BP (average of 3 measurements) at the time corresponding to AM dose (≤ 15 minutes) on Day 1
- Supine-to-standing (orthostatic) pulse and BP
 - at the time corresponding to AM dose (≤ 30 minutes) on Day 1 and at 1 and 4 hours (± 5 minutes) after that time
 - at the time corresponding to PM dose (≤ 15 minutes) on Day 1 and at 1 and 4 hours (± 5 minutes) after that time (Note: Supine-only pulse and BP may be taken at the 4-hour post PM dose timepoint if, in the Investigator's clinical opinion, earlier orthostatic pulse and BPs indicate it is safe to eliminate the standing [orthostatic] pulse and BP measurement.)
- ABPM starts at the time corresponding to AM dose (≤ 15 minutes)
- AE evaluation
- Concomitant medication recording

3.8.2.3 Day 1

- Respiratory rate and oral temperature AM predose (≤ 30 minutes)
- Oral temperature at 1 and 4 hours (± 30 minutes) AM postdose
- 12-lead ECG predose (≤ 30 minutes) and at 4 hours (± 15 minutes) postdose
- Supine-to-standing (orthostatic) pulse and BP
 - AM predose (≤ 30 minutes) and at 1, 4 and 8 hours (± 5 minutes) postdose

- PM predose (\leq 15 minutes) and at 1 and 4 hours (\pm 5 minutes) postdose
(Note: Supine-only pulse and BP may be taken at the 4-hour post PM dose timepoint if, in the Investigator's clinical opinion, earlier postdose orthostatic pulse and BPs for the given dosing and for previous measurements at the 4-hour postdose timepoint indicate it is safe to eliminate the standing (orthostatic) pulse and BP measurement.)
- Collection of blood samples for:
 - PK
 - AM predose (\leq 15 minutes) and at 1, 3, and 6 hours (\pm 5 minutes) postdose
 - PM predose (\leq 5 minutes) and at 1 and 3 hours (\pm 5 minutes) postdose
 - Serum creatinine AM predose (\leq 15 minutes)
 - Hemoglobin A1c AM predose (\leq 15 minutes)
 - Fasting plasma glucose AM predose (\leq 15 minutes)
 - Fasting plasma insulin AM predose (\leq 15 minutes)
 - Platelet function assessments AM predose (\leq 15 minutes)
 - [REDACTED]
- Randomization

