7.9.2 Clinical Laboratory Parameters

For each quantitative clinical laboratory parameter, descriptive statistics of the observed values (in derived SI units) as well as change from study baseline will be presented overall for each assessment timepoint for the safety population.

Parameter values will also be categorized as low, normal, or high based on reference ranges provided by the lab, and shifts from baseline to each later timepoint will be tabulated. If there is more than one measurement for a lab parameter at a postbaseline timepoint, only the last measurement will be used.

Listings of laboratory parameters will be included.

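### The ECG interpretation shift table goes only to Day 15 and omits the Day 1 4-hour ECG, the only one scheduled within 12 hours after an active dose

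*SAP*

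**What the plan says.** SAP 7.9.6 plans three ECG outputs:

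- For each ECG parameter, observed values are summarised, and "change from study baseline will be presented overall for each assessment timepoint for the safety population".
- The overall interpretation has three grades: normal; abnormal but not clinically significant; abnormal and clinically significant. It gets "Shift tables from study baseline to the discharge visit (Day 15) for the overall ECG interpretation", for all subjects in the Safety Population.
- "ECG parameters will also be presented in a data listing".

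Protocol 3.8.2.3 (Day 1) schedules a "12-lead ECG predose (≤ 30 minutes) and at 4 hours (± 15 minutes) postdose". The Schedule of Events ties the 4-hour recording to the morning dose. Protocol 3.8.2.11 lists a further ECG at discharge on Day 15, with no clock time of its own.

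For laboratory grades, SAP 7.9.2 is broader: "shifts from baseline to each later timepoint will be tabulated". Protocol 3.9.3.4.2 asks for ECG results, and their change from study baseline, at each postdose timepoint by treatment group. It does not ask for a shift table.

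**The concern.** The shift table is the only place where the graded ECG interpretation is tabulated, and it uses only the ECG at the end of the last dosing interval. A patient graded normal before dosing, abnormal at 4 hours and normal on Day 15 falls in the normal-to-normal cell. A patient with a valid 4-hour ECG but no Day 15 ECG contributes nothing.

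The study's objective is to compare the safety and tolerability of two regimens. On the morning of Day 1 one active arm takes 40 mg and the other 20 mg. By Day 15 both have had a week of the same 40 mg morning dose. The omitted recording is therefore the only post-dose ECG taken while the regimens differ. The SAP gives no reason for leaving it out, either in 7.9.6 or in Section 8.

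**Working it through.** **1. ECGs scheduled** (both Schedules of Events; Protocol 3.8)

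| ECG | Relation to dosing | In shift table |
|---|---|---|
| Screening, Check-in (Day -2) | before dosing | no |
| Day 1 predose | within 30 min before first dose; study baseline if not missing (SAP 6.1) | as baseline |
| Day 1, 4 h | 4 h ± 15 min after the morning dose, so 3.75 to 4.25 h | no |
| Day 15 | no stated time | yes |

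None is scheduled on Days 2 to 14, Day 21 or Day 42. There are two post-dose timepoints, and the table uses one.

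**2. How far Day 15 is from active drug**

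Protocol 3.3 says patients are followed in the clinic for 24 hours after the last dose. To reproduce that figure:

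- Protocol 3.5.5: "all patients will receive 2 daily 8-tablet doses (AM and PM), 12 hours" apart, ± 30 min.
- Protocol 3.5.3: "QD for both weeks or BID for the 1st week and QD the 2nd week". Protocol Table 3 shows the evening tablets in week 2 are placebo in every arm, so the last active dose is Day 14 morning.
- Protocol 3.8.2.11: the timed Day 15 assessments are 12 h ± 15 min after the evening dose.

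Nominal interval: 12 + 12 = 24 h. Shortest: 11.5 + 11.75 = 23.25 h. Longest: 12.5 + 12.25 = 24.75 h.

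The 24 h is reproduced when counted from the last active dose; from the last tablets taken (placebo) it is 12 h. SAP Table 3 agrees, since it labels the Day 14 end-of-interval PK sample as 24 hours postdose. Because the Day 15 ECG is untimed, applying 24 h to it is an inference from the assessments around it.

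**3. Size of the omission**

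With 26 patients at 5:5:3 (sum 13):

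- each active arm: 26 × 5/13 = 10
- placebo: 26 × 3/13 = 6

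One omitted ECG per patient gives up to 26 patient-ECGs. At most 10 + 10 = 20 follow an active dose (10 after 40 mg, 10 after 20 mg), and 6 follow placebo. These are maxima that assume complete data.

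**4. Where the 4-hour ECG is still reported**

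| Output | Contains the 4-h ECG? |
|---|---|
| Parameter summaries (SAP 7.9.6, statistics in 6.1) | yes: mean, SD, median, quartiles, minimum, maximum |
| ECG parameter listing (SAP 7.9.6) | yes |
| Adverse event tables (Protocol 3.7.3.9; SAP 7.9.1) | only if clinically significant and/or needing intervention |
| Notable-value table (SAP Table 4) | no: blood pressure and pulse only |
| Interpretation shift table (SAP 7.9.6) | no |

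The graded interpretation at 4 hours is tabulated nowhere. The patients who drop out of every categorical table are those whose 4-hour change was judged not clinically significant, needed no intervention and had gone by Day 15.

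**The case against.** The case for leaving the SAP alone has several parts.

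- **The data are reported.** The 4-hour summaries include the minimum and maximum of each parameter and of its change, so an extreme individual value is visible, and the values are listed. This stands. A reader might infer that only means are given at 4 hours and that individual abnormality is hidden; SAP 6.1 does not support that. But extremes of numeric parameters are not the graded interpretation.
- **Clinically significant changes have another route.** They become adverse events and, on Day 1, would appear in the Week 1 treatment-emergent summary by treatment group. This stands and narrows the gap to the group described above.
- **Day 15 may be the more informative ECG.** A reader might infer that the 4-hour ECG is the one most likely to show an acute drug effect. The documents give no Tmax, half-life or ECG effect data to support this. SAP Section 8 says a 24-hour profile does not adequately characterise the half-life, and accumulation ratios are planned. As an illustration, assume one compartment, rapid absorption and steady state. With x the fraction of drug remaining after 24 h, the trough on 40 mg daily equals the peak after a first 40 mg dose when x/(1 − x) = 1, so x = 1/2 and the half-life is 24 h. Against a first 20 mg dose, 2x/(1 − x) = 1, so x = 1/3 and the half-life is 24 × ln 2/ln 3, about 15 h. With longer half-lives Day 15 has the higher exposure. That justifies keeping Day 15, but not dropping the other timepoint.
- **The laboratory comparison is weak.** After dosing starts, the full laboratory panels are scheduled only on Day 15 and Day 42, so laboratory shifts contain no acute timepoint either. This stands as far as it goes. The SAP's general habit is still to use every post-baseline assessment: orthostatic criteria count any postdose timepoint (7.9.5), and notable values use all assessments including unscheduled ones (9.1).
- **Nothing required is missing.** The protocol asks for no shift table, and the study is exploratory and descriptive. This stands: it is an analysis choice, not a departure from the protocol.

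**Conclusion.** The point holds as a minor gap in tabulation. The only categorical ECG table covers one of the two post-dose timepoints. It omits the only ECG scheduled within 12 hours after an active dose, which is also the only post-dose ECG taken while the active regimens differ. The omission is up to 26 patient-ECGs, at most 20 of them after active drug. No sample size, power or error rate is affected.

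The statement about 12 hours assumes that the untimed Day 15 ECG is done alongside the timed Day 15 assessments. A reader might go further and call the 4-hour ECG the only one within 24 hours of an active dose. The documents do not establish that, because the inferred Day 15 range starts at 23.25 hours.

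A related point decides whether an added panel would be useful. SAP 7.9.6 describes its ECG summaries as overall and its shift table as covering all subjects, which reads as pooling drug with placebo. Protocol 3.9.3.4.2 requires treatment groups. The general rule in SAP 6.1 (by treatment group unless otherwise indicated) may be meant to apply, but the wording of 7.9.6 can be taken as indicating otherwise. The passages should be reconciled.

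**What to change.** In SAP 7.9.6:

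1. Tabulate shifts in overall ECG interpretation from study baseline to Day 1 4 hours, to Day 15, and to the worst post-baseline interpretation. Define worst by the order of the three grades, and let it include unscheduled ECGs, in line with SAP 9.1.
2. Present the shift tables and the ECG parameter summaries by treatment group, using the columns in SAP 6.1 (placebo, BID/QD, QD/QD, IW-1973 overall), so that the section agrees with Protocol 3.9.3.4.2.

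The cost is a short SAP edit and a few extra table panels. The ECGs are already scheduled, so no visit, procedure or patient is added.
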